### 6.5.2. Safety Laboratory Evaluation

Individual results of safety laboratory tests from hematology, chemistry, and urinalysis that meet Takeda's markedly abnormal criteria will be summarized and listed.

Baseline, postdose, and change from Baseline to postdose laboratory data will be summarized at each scheduled visit (Table 6.c).

All clinical laboratory data (Table 6.c) will be listed.

**Table 6.c Safety laboratory test**

Laboratory Test	Sample	Visit
Hematology	RBC	Visit1, 4, 6, 8, 11
	WBC	Follow-up visit
	Hemoglobin	Unscheduled Visit
	Hematocrit	
	Platelets	
Clinical Chemistry	ALT	Visit1, 4, 6, 8, 11
	Albumin	Follow-up visit
	Alkaline phosphatase	Unscheduled Visit
	AST	
	Total bilirubin	
	Total protein	
	Creatinine	

	Blood urea nitrogen Creatine kinase GGT Potassium Sodium Glucose Chloride Bicarbonate Calcium Magnesium	
Urinalysis	pH Protein Glucose Blood Nitrite Microscopic Analysis (only if positive dipstick results): RBC/high power field WBC/high power field Epithelial cells, casts etc	Visit1, 6, 11 Unscheduled Visit

### 6.5.3. Vital Signs

Vital signs include body temperature, respiratory rate, systolic blood pressure, diastolic blood pressure and pulse at each visit including scheduled visit (visit 1, 2, 3, 4, 5, 6, 7 8, 9, 10, 11, follow-up visit) and unscheduled visit.

Individual results of vital signs that meet Takeda's markedly abnormal criteria will be summarized and listed.

Baseline, postdose, and changes from Baseline in vital sign measurements will be summarized at each scheduled visit.

All vital sign data will be provided in the data listings.

### 6.5.4. Height, Weight and BMI

Baseline, postdose, and changes from Baseline in height, weight and BMI measurements will be summarize at each scheduled visit.

All data for height, weight, BMI will be provided in the data listings.

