- The subject or the subject's parent(s) or legally acceptable representative signs and dates a written informed consent form and any required privacy authorization prior to the initiation of any study procedures.
- The subject has onset of appearance of secondary sexual characteristic earlier than age 8.0 years in girls or earlier than 9.0 years in boys and the symptom is persistent, and has confirmed diagnosis of CPP.
- The subject has basal LH level >5.0 IU/L or peak LH >5.0 IU/L in stimulation test OR peak LH >3.3 IU/L with LH/follicle-stimulating hormone (FSH) >0.6 in stimulating test. The subject has evidence of gonadal development evaluated by ultrasonography: multiple ovarian follicles ≥ 4 mm in any ovary OR uterine enlargement in females or testicular volume ≥ 4 mL in males.
- The subject has advanced bone age (BA) ≥ 1 year and BA is ≤ 11.5 years in females or ≤ 12.5 years in males or predicted adult height <150 cm in females or <160 cm in males OR SDS <-2 standard deviations (SD) OR rapid growth defined as growth of BA/growth of chronologic age >1 . BA is determined by Greulich and Pyle standards or Tanner-Whitehouse 3 (TW3) standards.
- The subject has anticipated treatment duration of at least 2 year in investigator's judgment.

Main Criteria for Exclusion:

- The subject has received any investigational compound within 30 days prior to screening.
- The subject has received gonadotropin-releasing hormone analog (GnRHa) treatment in a previous clinical study or as a therapeutic agent.
- The subject is an immediate family member, study site employee, or is in a dependant relationship with a study site employee who is involved in the conduct of this study (eg, spouse, parent, child, sibling) or may consent under duress.
- The subject has any findings in his/her medical history, physical examination, or safety clinical laboratory tests giving reasonable suspicion of underlying disease that might interfere with the conduct of the trial.
- The subject has any concomitant medical condition that, in the opinion of the investigator, may expose a subject to an unacceptable level of safety risk or that affects subject compliance.

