9.1.13 Bone Mineral Density

Bone mineral density will be evaluated by dual energy x-ray bone densitometry at selected sites only. Throughout the study, the same apparatus should be used and operated in the same scan mode for all scans for an individual subject. The results will be recorded in the eCRF.

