#### **2.2.3. Additional Endpoints**

- Percentage of subjects with suppression of peak luteinizing hormone (LH) and follicle-stimulating hormone (FSH) to pre-pubertal levels in stimulation test at Week 96.
- Percentage of subjects with suppression of basal estradiol level in female subjects or testosterone level in male subjects to pre-pubertal level at Week 96.
- Percentage of subjects with improvement in predicted adult height at Week 96 compared with Baseline.
- Percentage of subjects with a decrease in the ratio of bone age (BA) to chronological age at Week 96 compared with Baseline.

- Change in laboratory values including changes in chemistry, hematology and bone metabolism biomarkers.
- Change in body mass index (BMI).
- Change in bone mineral density.
- Incidence of polycystic ovarian syndrome in female subjects.

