#### 6.2.2. Definition of Baseline and Change from Baseline

Baseline is defined as the last non-missing measurement prior to first dose of study drug.

The change from baseline will be calculated by subtracting the baseline values from the individual post-baseline values. If either the baseline or post-baseline value is missing, the change from baseline is set to missing as well.

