### **6.6. Other Analyses**

The serum bone metabolism biomarkers including phosphorus, 25-hydroxy vitamin D, osteocalcin, crosslaps will be summarized at each scheduled visit (visit 2, 11) by Baseline, postdose and changes from Baseline, individual data will be listed.

Baseline, postdose, and changes from Baseline in bone mineral density measurements will be summarized at each scheduled visit (visit 2, 11). All bone mineral density data will be provided in the data listings.

Pelvic and testicular ultrasonography will be summarized at each scheduled visit (visit 1, 4, 6, 8, 10, 11, follow-up visit) and data will be provided in listings.

Other Variables:

The physical examination findings will be presented in data listings.

The urine pregnancy test, cranial magnetic resonance imaging (MRI), carcino-embryonic antigen (CEA), alpha-fetoprotein (AFP) and beta human chorionic gonadotropin ( $\beta$ -HCG) at Screening will be summarized and listed.

---

Data collected during the observational follow-up phase will be summarized and individual data will be listed.

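### BMI and bone mineral density are summarised only as plain change from Baseline in growing children with no control arm, so normal growth cannot be separated from any other change

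*SAP*

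**What the plan says.** SAP 6.5.4 covers height, weight and BMI: "changes from Baseline in height, weight and BMI measurements will be summarize at each scheduled visit". SAP 6.6 covers BMD: "changes from Baseline in bone mineral density measurements will be summarized at each scheduled visit (visit 2, 11"). SAP 6.2.2 defines the calculation: "The change from baseline will be calculated by subtracting the baseline values from the individual post-baseline values". Protocol 13.1.4.4 and 13.1.5 describe the same summaries, so the two documents agree.

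SAP 2.2.3 lists change in BMI and "Change in bone mineral density" as additional endpoints. Height and weight are not endpoints.

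Under SAP 6.1, summaries are given for males, females and all subjects. Nothing divides them by age, bone age or pubertal stage. Neither document plans an SDS, Z-score or percentile, or names an external reference, for any of the four measures.

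For BMD, Protocol 9.1.13 says: "Bone mineral density will be evaluated by dual energy x-ray bone densitometry at selected sites only". It keeps the apparatus and scan mode constant within a subject but does not standardise across sites, and it gives no unit or scale.

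**The concern.** Subjects enter after onset of secondary sexual characteristics before 8.0 years (girls) or 9.0 years (boys) and are followed for almost two years. Height, weight, BMI and BMD can all be expected to move over that time without any drug. There is no untreated group, and the plan names no external reference to stand in for one. A mean change from Baseline then mixes ordinary growth with whatever else happened, and the tables offer no way to divide the two.

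Two misreadings are at stake. A rise in BMI that only follows age could be read as weight gain on treatment. More seriously, slowed bone accrual could appear as a positive change in BMD and look reassuring. This matters because safety is the primary objective, Protocol 4.2 gives the lack of long-term data in China as the rationale, and the results go to the CFDA.

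**Working it through.** The plan gives no figure to reproduce. The sample size of about 300 has no effect size or SD behind it, and the documents give no growth rates. The figures below are therefore illustrations on assumed rates, treated as linear over time.

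**Inputs from the documents.** Treatment runs to Week 96 (Day 672 in SAP Table 6.a). The closing BMD scan is at Week 100 (Day 700).

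- 672 / 365.25 = 1.84 years
- 700 / 365.25 = 1.92 years (1.916)

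**Formula.** With no drug effect, mean raw change = yearly growth × elapsed years.

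**BMI, assumed rise of 0.2 to 0.6 kg/m² per year.**

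- 0.2 × 1.84 = +0.37 kg/m²
- 0.6 × 1.84 = +1.10 kg/m²

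**BMD in absolute units, assumed normal gain of 2 to 5% per year.**

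- 2% × 1.916 = +3.8%
- 5% × 1.916 = +9.6%
- Less a 3-point deficit: 3.8 − 3 = +0.8%, and 9.6 − 3 = +6.6%

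The table would show a gain at every rate in that range. A 3-point deficit would show as a loss only if normal gain were below 3 / 1.916 = 1.6% per year.

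**BMD, deficit as a share of normal gain.** Take 4% per year, so expected growth is 4 × 1.916 = 7.7%.

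| Share of gain lost | Raw change shown | Shortfall (points) |
|---|---|---|
| 25% | +5.7% | 1.9 |
| 50% | +3.8% | 3.8 |
| 75% | +1.9% | 5.7 |

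The raw change stays positive in every row. This is a bias, so it does not depend on how many subjects are scanned, a number the documents do not give.

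**What standardising does.** A child who tracks an age- and sex-specific reference has, by construction, a change in SDS or Z-score of zero, while the raw change equals the growth over the period. The size of the standardised change in this trial cannot be computed, because the documents contain no reference data.

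**The case against.** The strongest reply is that the plan is descriptive and claims nothing. A reader might infer that normal growth will be reported as leuprorelin's effect. The documents do not support that: SAP 4 says the study is not powered for any hypothesis test, and no section attributes these changes to the drug. That reply stands. What remains is that two named endpoints are summarised on a scale that cannot separate growth from anything else.

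Other limits also stand:

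- **BMD scale.** It is not stated, so one cannot say that BMD will be analysed in raw units. The masking calculation applies only if it is.
- **Intervals.** It is tempting to say that a confidence interval for BMI change would exclude zero through growth alone. SAP 6.4 plans 95% intervals only for the binary efficacy variables, and none is planned for these means.
- **SDS at entry.** A reader might infer that the analysis discards standardised values already in use. The only SDS is one branch of inclusion criterion 5, "OR SDS <-2 standard deviations (SD"), which names neither the measure nor the reference. The SAP follows the protocol here and has dropped nothing.
- **Growth as efficacy.** Predicted adult height and the ratio of bone age to chronological age (SAP 6.4) take maturation into account. They cover height and skeletal maturation, but neither tells us about BMI or BMD.
- **Standardising is not a control arm.** Subjects may enter with bone age advanced by a year or more, so they need not track a chronological-age reference even untreated. Protocol 4.1 describes slower growth and bone maturation as a consequence of suppression, so a falling height SDS could be the intended effect. This limits what SDS can show, but it does not make plain change more informative.

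Standardised scores could also be added later from the listed data. That is true, but prespecifying the reference avoids choosing it after the results are seen.

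**Conclusion.** The point holds for the BMI and BMD endpoints and, as supportive measures, for height and weight. Plain change over 1.84 to 1.92 years, split only by sex and without a comparator, cannot separate normal growth from other change. On assumed rates, growth alone gives about +0.4 to +1.1 kg/m² in BMI and, in absolute units, +3.8% to +9.6% in BMD, which is enough to hide a 3-point BMD deficit. These sizes rest wholly on the assumed rates. The absence of any age-standardised summary and the unstated BMD scale can be read directly from the documents.

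The documents do not support a claim that the plan presents growth as a drug effect. Nor would standardised scores turn a single-arm change into an estimate of that effect. This is a worthwhile, low-cost improvement to additional endpoints. It does not affect the primary or secondary endpoint.

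**What to change.** In SAP 6.5.4 and 6.6:

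1. Derive age- and sex-specific SDS for BMI, with height and weight as supportive, at Baseline and each scheduled visit. Derive BMD Z-scores at Baseline and Visit 11. Name one reference for each measure.
2. Report mean change in SDS or Z-score with a 95% CI beside the raw values.
3. State the scale on which BMD is recorded and summarised.
4. Add a supportive bone-age- or height-adjusted version. Bone age is scheduled at Week 96 but not at Week 100, so say which reading is paired with the Visit 11 scan.
5. State that neither raw nor standardised change in this single arm estimates the drug effect.

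**Cost.** This needs SAP wording and one derivation per measure. Date of birth, sex, height, weight and bone age are already collected, and SAP 6.4 already defines untruncated decimal age, so no new assessment is needed for the SDS. The real burden is choosing the references. The BMD reference must suit the scanners at the selected sites, and the documents do not identify those.

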### **6.5.5. ECG**

A standard 12-lead ECG will be recorded at each scheduled visit (visit 1, 3, 5, 7, 10, follow-up visit) and unscheduled visit. The investigator (or a qualified observer at the investigational site) will interpret the ECG within normal limits (Normal), abnormal but not clinically significant (Abnormal, NCS), or abnormal and clinically significant (Abnormal, CS).

Individual results of quantitative ECG parameters from the 12-lead safety ECGs that meet TDC's markedly abnormal criteria will be summarized and listed. Analysis of central tendency for QT/corrected QT interval (QTc) and categorical analysis of QT/QTc will be performed.

Baseline, postdose, and changes from Baseline for QT/corrected QT interval (QTc) will be summarized at each scheduled visit (visit 1, 3, 5, 7, 10, follow-up visit).

Shift tables will be generated for the investigator's ECG interpretations(Normal, Abnormal and NCS, Abnormal and CS) that changed from Baseline to the postdose collections by above groups at each scheduled visit (visit 1, 3, 5, 7, 10, follow-up visit).

All ECG data will be provided in the data listings.

### **6.6. Other Analyses**

The serum bone metabolism biomarkers including phosphorus, 25-hydroxy vitamin D, osteocalcin, crosslaps will be summarized at each scheduled visit (visit 2, 11) by Baseline, postdose and changes from Baseline, individual data will be listed.

Baseline, postdose, and changes from Baseline in bone mineral density measurements will be summarized at each scheduled visit (visit 2, 11). All bone mineral density data will be provided in the data listings.

Pelvic and testicular ultrasonography will be summarized at each scheduled visit (visit 1, 4, 6, 8, 10, 11, follow-up visit) and data will be provided in listings.

Other Variables:

The physical examination findings will be presented in data listings.

The urine pregnancy test, cranial magnetic resonance imaging (MRI), carcino-embryonic antigen (CEA), alpha-fetoprotein (AFP) and beta human chorionic gonadotropin ( $\beta$ -HCG) at Screening will be summarized and listed.

---

Data collected during the observational follow-up phase will be summarized and individual data will be listed.

### **6.7. Interim Analyses**

One interim analysis will be performed after Week 100(visit 11). All available efficacy and safety data will be evaluated and reported to CFDA. The study will be continued to the observational safety follow-up phase.

## Appendix A Schedule of Study Procedures

Study Day/Week:	Screening	Treatment										Final safety Visit/ Early Termination Visit Week 100 (b)	Observational Follow-up visit (c)
	Days -28 to -1	Wk 0/ Day 1/first dose (a)	Wk 12	Wk 24	Wk 36	Wk 48	Wk 60	Wk 72	Wk 84	Wk 96/ last dose			
Visit Windows (Days):	NA	NA	±5d	±5d	±5d								
Visit Number:	1	2	3	4	5	6	7	8	9	10	11		
Informed consent	X												
Inclusion/exclusion criteria	X												
Demographics and medical history	X												
Medication history	X												
Physical examination	X					X						X	X
Vital signs	X	X	X	X	X	X	X	X	X	X	X	X	X
Weight and height	X	X	X	X	X	X	X	X	X	X	X	X	X
Concomitant medications	X	X	X	X	X	X	X	X	X	X	X		
Concurrent medical conditions	X												
Predicted adult height (d)	X					X				X			X
Tanner staging evaluation	X	X	X	X	X	X	X	X	X	X	X	X	X
Bone age (e)	X			X		X		X		X			X
Hematology	X			X		X		X				X	X
Urine analysis	X				X							X	
Urine Pregnancy test (f)		X											
Pregnancy avoidance counseling	X	X	X	X	X	X	X	X	X	X	X		
Clinical chemistry	X			X		X		X				X	X
ECG	X		X		X		X				X		X
Pelvic/Testicular ultrasonography (g)	X			X		X		X		X	X		X
LH and FSH					X		X		X				
Estradiol or Testosterone		X(j)	X	X	X	X	X	X	X	X	X		X
Stimulation test (h)	X		X							X			
Cranial MRI (i)	X												
CEA, AFP, $\beta$ -HCG	X												
Bone mineral density (j)		X (j)										X	
Serum bone metabolism biomarker (k)		X(j)										X	
Injection investigational drug (l)		X	-----	-----	-----	-----	-----	-----	-----	X			
PTE assessment	X	X											

AE assessment		X	X	X	X	X	X	X	X	X	X	X
---------------	--	---	---	---	---	---	---	---	---	---	---	---

NA=not applicable.

(a) The day of first investigational drug administration for Treatment period is Day 1. The day before first investigational drug administration for Treatment period is Day -1.

(b) Conduct Final Visit procedures for subjects discontinued early per Section **Error! Reference source not found.** The end of study is defined as the date of the last visit (Week 100) of the last subject undergoing the study unless the study is stopped earlier by sponsor due to futility or for safety reasons. Subjects who discontinued from the study for any reason will complete the Early Termination Visit/Final Safety Visit, 4 weeks after the last dose of leuprorelin.

(c) During the observational follow- up period, it is recommended to monitor the subjects who remain on treatment at least every 6 months or at a schedule based on the investigator's judgments until drug discontinuation to collect the following: height and weight, secondary sexual characteristics, hematology, clinical chemistry, ultrasonography, LH and FSH, estradiol or testosterone and ECG. ECG will also be performed 4 weeks after the last administration of leuprorelin. All subjects will be followed up annually after the last dose of leuprorelin until stable puberty is reached. At each visit, the following will be performed: Tanner staging, height and weight, BMI, menstrual history, and pelvic ultrasonography for girls. Stable puberty is defined as 2 years after menarche for girls or Tanner staging V of secondary sexual characteristics development for boys.

(d) Predicted adult height will be evaluated using Bayley-Pinneau method.

(e) Bone age will be evaluated by investigators at each site using TW3 standards or Greulich-Pyle standards at Screening. All bone age x-ray will be sent for central reading before the end of the study

(f) The female subject who, at the discretion of the investigator, is deemed to be of child bearing potential must provide negative urine pregnancy test at Day -1 or Day 1 prior to drug administration.

(g) Pelvic ultrasonography will be performed for females to measure, uterus size and number/size of follicles. For males, ultrasonography will be performed to measure the testicular volume. These results if available already can be used as part of screening. If result is already available – whether at same site or hospital – within 28 days prior to first dose, the result can be used for screening, under the condition that the Site retains a copy of the data in file notes as source documents.

(h) F test: Blood samples will be collected at 0, 30, and 60, minutes after the injection of GnRH. It is acceptable to use both GnRH and GnRHa in stimulation test; however, it is preferable to use GnRH as priority. These results if available already can be used as part of screening. If stimulation test result is already available – whether at same site or hospital – within 28 days prior to first dose, the result can be used for screening, under the condition that the Site retains a copy of the data in file notes as source documents. (i) Cranial MRI can consist of only pituitary scan, including saddle region.

(j) Bone mineral density will be evaluated by dual energy x-ray bone densitometry at selected sites, which can done at any time prior to the first dose after the Screening. Estradiol or Testosterone and Serum bone metabolism biomark also can be done at any time prior to first dose as part of screening visit. (k) Serum bone metabolism biomarker included phosphorus, 25-hydroxy vitamin D, osteocalcin, crosslaps. These 4 tests can be performed as per what is available at the given Site. These tests can done at any time prior to the first dose after the Screening.

(l) Subcutaneous injection Leuprorelin every 4 weeks. For the dosing visits between Visits 2-3, between Visits 3-4, between Visits 4-5, between visits 5-6, between visits 6-7, between 7-8, between 8-9, between visits 9-10: these visit window is +/- 2 days; in addition, the between gap between dosing cannot be less than 3 weeks (21 days).
